12.3. Deaths and Serious Adverse Events

All SAEs will be summarized in a manner similar to that described above for the overall AE summary by treatment group. By-subject listings of all non-fatal SAEs and all deaths will be presented.

12.4. Adverse Events Leading to Discontinuation of Investigational Product and/or Withdrawal from the Study and Other Significant Adverse Events Incidents

12.4.1. Post-injection Systemic Reactions

Systemic reactions will be collected on the 'Injection Site Reaction' page of the CRF over the same time period as stated above for AEs. Symptoms will also be recorded on the AE form and identified by MedDRA preferred term (PT). A summary of the number and percentage of subjects with a post-injection systemic reaction and the number of reactions, the symptoms associated with the reaction (e.g. fever and chills), whether a subject had any medications administered for a reaction and whether a subject had an event meeting anaphylaxis criteria will be presented by treatment group for the on-therapy period.

Systemic Injection reactions are defined as those with AETERM in ('ABDOMINAL PAIN', 'CHILLS', 'FEVER', 'HEADACHE', 'NAUSIA', etc..) all the systemic symptoms as per listed in the 'Post-injection Systemic reactions' page of the CRF.

A by-subject listing of post-injection systemic reactions will be presented.

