12.4.2. Local Reactions

Local reactions will be collected on the 'Injection Site Reaction' page of the CRF over the same time period as stated above for AEs. Symptoms will also be recorded on the AE form and identified by MedDRA preferred term (PT). A summary of the number and percentage of subjects with a local reaction and the number of reactions, the symptoms associated with the reaction (e.g. erythema and swelling), whether a subject had any medications administered for a reaction will be presented by treatment group for the on-therapy period.

Systemic Injection reactions are defined as those with AETERM in ('ERYTHEMA', 'BLEEDING', 'ITCHING', 'EDEMA', 'PAIN', 'SWELLING' etc..) all the local symptoms as per listed in the 'Post-injection local reactions' page of the CRF.

A by-subject listing of local reactions will be presented.

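### The SAP defines injection reactions by a match on adverse-event term across the whole on-therapy period, without requiring a reaction-page record, and labels the local-reaction rule systemic

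*SAP*

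**What the plan says.** SAP 12.4.1 begins with the data source: "Systemic reactions will be collected on the 'Injection Site Reaction' page of the CRF over the same time period as stated above for AEs". It adds that symptoms also go on the adverse-event form and are identified by MedDRA preferred term. The operational rule then begins "Systemic Injection reactions are defined as those with AETERM in" and gives an open-ended list: abdominal pain, chills, fever, headache and NAUSIA. The list is explained as "all the systemic symptoms as per listed in the 'Post-injection Systemic reactions' page of the CRF".

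SAP 12.4.2, headed Local Reactions, has the same structure. Collection is described as "Local reactions will be collected on the 'Injection Site Reaction' page of the CRF over the same time period as stated above for AEs". The rule reads "Systemic Injection reactions are defined as those with AETERM in ('ERYTHEMA', 'BLEEDING', 'ITCHING', 'EDEMA', 'PAIN', 'SWELLING' etc", and the list is tied to "all the local symptoms as per listed in the 'Post-injection local reactions' page of the CRF".

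Both tables are to be presented by treatment group for the on-therapy period. SAP 9.3.2 defines that period as running from the start of study medication to 4 weeks after the last dose. Protocol 6.3 lists the frequency of systemic reactions after injection and of injection site reactions among its safety endpoints, and Protocol 8.3.6.9 asks for summaries of both by treatment group.

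**The concern.** The rule that a programmer would implement is a term match. Neither section says that a counted event must have a record on a reaction page. Neither sets a time limit after an injection other than the on-therapy period. The local rule does not say that pain, itching or swelling must be at the injection site. Headache, fever and pain are common complaints over more than a year of follow-up, so a match against all adverse events could count events that have nothing to do with an injection.

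The opposite error is also possible. A true reaction whose recorded wording differs from the listed term would fail the match. Each section also names two identifiers, preferred term and AETERM, and the local rule carries the wrong label. Two programmers could follow this text faithfully and produce different tables for safety outcomes that the protocol names.

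**Working it through.** The plan gives no figure for this point, so there is none to reproduce. The check is a reading of the two sections against SAP 9.3.2 and Protocol 6.3.2.3, followed by two small illustrations.

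**1. What the rule requires.**

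| Requirement | Systemic (12.4.1) | Local (12.4.2) |
|---|---|---|
| Reaction page named as place of collection | yes | yes |
| Reaction page named as source of the term list | yes | yes |
| Counted event must have a reaction-page record | not stated | not stated |
| Time limit after an injection | on-therapy period only | on-therapy period only |
| Event must be at the injection site | not applicable | not stated |
| Identifier | preferred term, then AETERM | preferred term, then AETERM |
| Label in the defining sentence | systemic | systemic |

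Read literally, the last row gives systemic reactions two definitions and local reactions none.

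**2. Page names.** SAP 12.4.1 uses two names, one for the page of collection and another for the page that supplies the terms. SAP 12.4.2 does the same, with a different second name. Protocol 6.3.2.3 refers to a Postinjection Systemic Reaction eCRF page. The text leaves unclear whether there is one shared page or two.

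**3. Exact matching on the printed terms.** I take AETERM in its usual sense, as the term reported by the site; the SAP does not define it.
- HEADACHE and FEVER match the systemic list whatever their cause or timing.
- A bare PAIN matches the local list wherever it occurs.
- INJECTION SITE PAIN and INJECTION SITE ERYTHEMA match neither list.
- NAUSEA matches neither list, because the printed term is NAUSIA.

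Both lists are left open-ended, so the complete set of terms cannot be checked from the documents.

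**4. How wide the time limit is.** For a subject who completes dosing, the on-therapy period is about 56 × 7 + 1 + 28 = 421 days. SAP section 3 gives 15 dosing visits. The documents give no reaction window, so the windows below are assumptions.

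| Assumed window per visit | Days covered | Share of 421 days |
|---|---|---|
| 1 day | 15 | 3.6% |
| 3 days | 45 | 10.7% |
| 7 days | 105 | 24.9% |

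Most of the period in which a term match would count is therefore not close to an injection. These shares describe time only. They do not estimate how many events would be misclassified, because no background rate is given.

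**5. Leverage of one subject.** SAP section 5 gives 69 randomized subjects. With a near-even split, an arm has about 69 / 2 = 34.5 subjects, so one misclassified subject moves an arm's percentage by about 1 / 34.5 = 2.9 points.

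**The case against.** The best defence is that the AETERM list only sorts reactions already recorded on the reaction page. If both types are collected on one page, something has to separate systemic from local, and a term list could do it. Three features support this reading:
- The tables must report whether medication was given for a reaction and, for systemic reactions, whether anaphylaxis criteria were met. A bare term match cannot supply either.
- SAP 9.3.2 lists injection site reactions separately from adverse events when it assigns therapy periods.
- Protocol 6.3.2.3 has the investigator complete a systemic reaction page where applicable, so attribution is made when the event occurs.

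This reading is plausible, but it does not clear the text. The defining sentences themselves point to separate systemic and local pages, which would make a sorting list unnecessary. A filter on reported wording could still drop genuine page-recorded reactions. The conflict between preferred term and AETERM and the wrong label in 12.4.2 remain on either reading.

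Two further points stand. The label in 12.4.2 is almost certainly a copying slip, because the section heading, the terms and the page reference all say local. The stakes are also limited. The safety data receive no inferential analysis, all adverse events are tabulated and listed anyway, each reaction type has its own by-subject listing, and the SAP's shortened safety endpoint list in 2.2.4 no longer names injection reactions, although the tables in 12.4.1 and 12.4.2 remain.

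**Conclusion.** The stated rule is faulty and should be corrected. Programmed literally against all adverse events, it could count unrelated headache, fever or pain as injection reactions and miss true reactions worded differently. It would also leave local reactions without a definition of their own. The effect is confined to two descriptive safety tables in a trial that was terminated early. No efficacy result, significance level or power figure is affected.

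A reader might infer more than the documents support:
- **That the definitions have no link to the reaction page.** They name it as the place of collection and the source of the terms. What is missing is the requirement for a page record.
- **That both tables will be wrong.** They could be wrong if the rule is programmed as written. If they are built from the page, they need not be.
- **That nausea will be missed.** The misspelling sits in an open-ended list that refers to the CRF page for its full content, so this follows only from exact matching on the printed terms.
- **That about 89% to 96% of counted reactions would be background.** Those figures are the complements of the assumed 3-day and 1-day shares (1 − 0.107 and 1 − 0.036). They apply only to events already taken to be unrelated and occurring at a constant rate. They say nothing about the share of tabulated reactions that would be unrelated.

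The size of the error cannot be estimated from the documents.

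**What to change.** In SAP 12.4.1 and 12.4.2:
- Define systemic and local reactions as events recorded on the corresponding post-injection reaction CRF page, or adverse events linked to such a record.
- Use the MedDRA preferred term only to describe the symptoms of those events, and remove the AETERM match as the defining rule.
- Change the label in the 12.4.2 definition from systemic to local.
- Correct NAUSIA to nausea. If any term list is kept, print it in full.
- Use one set of CRF page names in both sections, matched to the eCRF and to Protocol 6.3.2.3.

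The cost is a short SAP edit and minor programming. The SAP describes the reaction-page data as already collected, so no new data are needed. If the tables have already been produced, the study report should state which rule was used.

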12.4.2. Local Reactions

Local reactions will be collected on the 'Injection Site Reaction' page of the CRF over the same time period as stated above for AEs. Symptoms will also be recorded on the AE form and identified by MedDRA preferred term (PT). A summary of the number and percentage of subjects with a local reaction and the number of reactions, the symptoms associated with the reaction (e.g. erythema and swelling), whether a subject had any medications administered for a reaction will be presented by treatment group for the on-therapy period.

Systemic Injection reactions are defined as those with AETERM in ('ERYTHEMA', 'BLEEDING', 'ITCHING', 'EDEMA', 'PAIN', 'SWELLING' etc..) all the local symptoms as per listed in the 'Post-injection local reactions' page of the CRF.

A by-subject listing of local reactions will be presented.

12.5. Pregnancies (as applicable)

A listing of subject pregnancies (if any) will be presented.

12.6. Clinical Laboratory Evaluations

Hematology, chemistry and urinalysis evaluations will be performed. Established or generally acknowledged methods, normal ranges, and quality control procedures will be supplied by [REDACTED] for the study records. All laboratory results will be presented in the International System of Units (SI).

During the study, investigators will not receive central laboratory data that have the potential to unblind a subject's treatment assignment. This includes lymphocytes, B-lymphocyte chemokine, BAFF, anti-Dsg autoantibodies, and HAHA.

After the Week 60 visit and each Individualized Follow-up visit, the central laboratory (or designee) will notify the investigator whether or not a subject needs to remain in follow-up or if the subject may be discharged from the study (based on B-lymphocyte counts and IgG levels, but the actual laboratory values will not be provided).

Hematology parameters collected will include platelet count, red blood cell (RBC) count, hemoglobin, hematocrit, white blood cell (WBC) count, WBC differential (neutrophils, lymphocytes, monocytes, bands, eosinophils, basophils), nucleated RBCs, CD19+B-lymphocyte counts, CD3, CD4, CD8 and CD4:CD8 ratio. Chemistry parameters collected will include total protein, albumin, alanine aminotransferase (ALT), aspartate aminotransferase (AST), alkaline phosphatase, gamma-glutamyl transferase, total bilirubin, blood urea nitrogen (BUN), creatinine, creatinine clearance (calculated), sodium, potassium, chloride, calcium, bicarbonate (carbon dioxide content) and glucose. Urinalysis parameters collected will include appearance, specific gravity, pH, protein, glucose, ketones, leukocyte esterase (leukocytes), hemoglobin (RBCs), microscopy (RBC/HPF, WBC/HPF, epithelial cells, trichomonas, bacteria, yeast, crystals, ammonia urates, mucous threads, amorphous sediment, casts, microalbumin, creatinine and microalbumin:creatinine ratio).

All hematology, chemistry and urinalysis laboratory parameters with a quantitative result will be summarized, for each treatment group, at every assessed time point using descriptive statistics. In addition, change from Baseline in these quantitative tests will be summarized by treatment group and at every assessed post-baseline time point.

All laboratory assessments will be summarized for the Safety population and will be presented in a data listing.

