6.3. Safety

The following safety endpoints will be assessed:

[figure not shown]
- Adverse events
- Adverse event frequency, severity, and relationship to investigational product
- Frequency and severity of infections
- Frequency of SAEs
- Frequency of withdrawals due to treatment-related AEs.
- Frequency of AEs leading to permanent discontinuation of investigational product.
- Frequency of AEs of special interest, postinjection systemic reactions, and injection site reactions.
- Change from baseline in vital signs.

- Frequency of vital signs of clinical concern.
- Change from baseline in laboratory (hematology, chemistry, and urinalysis) parameters.
- Frequency of laboratory (hematology, chemistry, and urinalysis) results of potential clinical concern.
- Immunogenicity as measured by the incidence, titer, and type of HAHA immune response.

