8.3.6.9. Safety Analyses

The analysis of safety data will use the Safety population. These data will not undergo any formal statistical analysis.

Adverse Events

Adverse events will be coded using the MedDRA and summarized by system organ class and preferred term.

Summaries by treatment groups, of the number and percentage of subjects with the following AEs will be provided:

- All AEs
- Adverse event frequency, severity, and relationship to investigational product
- Frequency and severity of infections
- Frequency of SAEs
- Percentage of subjects withdrawing due to AEs assessed by the investigators as at least possibly related to treatment
- Adverse events leading to permanent discontinuation of investigational product
- Adverse events of special interest (see Section 6.3.2.3)
- Postinjection systemic reactions
- Injection site reactions

The hierarchical relationship between MedDRA, system organ classes, and preferred terms and verbatim text will be displayed for relevant AEs.

Clinical Laboratory Evaluations

Summary statistics will be presented for each laboratory test, and change from baseline, at each assessment time point by treatment group. Laboratory test values will be flagged to show whether they are a value within, below, or above the normal range and if they are a value of potential clinical concern. The number and percentage of subjects with values in each of these categories at each assessment time point will be summarized for each laboratory test.

Vital Signs

Each variable and change from baseline in each variable will be summarized at each assessment time point by treatment group. In addition, the number and percentage of subjects with vital sign values within, below, and above values of potential clinical concern will be summarized for each variable.

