2.2.1. Co-Primary Efficacy Endpoints

Some of the analysis bullet points described in the original protocol is removed as requested by Novartis (section 2.2.2 - 2.2.6).

Two co-primary efficacy endpoints will be evaluated:

- Time to SR on minimal steroid therapy (defined as time from randomization to the time the subject initially tapered his/her oral prednisone/prednisolone dose to ≤ 10 mg/day and maintained ≤ 10 mg/day of oral prednisone/prednisolone with no new or nonhealing (established) lesions for ≥ 8 weeks AND maintained that status until Week 60).
- Duration of remission on minimal steroid therapy (defined as total time [sum] of all periods of remission while on minimal steroid therapy [oral prednisone/prednisolone dose of ≤ 10 mg/day] up to Week 60).

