2.2.4. Safety Endpoints

- All AEs
- Frequency of serious adverse events (SAEs).
- Change from Baseline in vital signs.
- Change from Baseline in laboratory (hematology, chemistry, and urinalysis) parameters.
- Immunogenicity as measured by the incidence, titer, and type of human anti-human antibody (HAHA) immune response.

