9.3.3. Visit Slotting Algorithm

For all safety and efficacy parameters to be summarized or analyzed by visit, data records will be slotted to one of the protocol specified visits using the following algorithm

- Determine the therapy period and study day for all records using the algorithms from Section 9.3.1 and Section 9.3.2.
- For all records (including unscheduled visit records, early withdrawal records and repeat visit records), use the therapy period and study day determined above with the slotting intervals in the analysis visit window table below to slot the record to the appropriate analysis visit.
 - For records determined to be during the pre-therapy period, the analysis visits will be based on the nominal visits recorded in the eCRF. The Baseline analysis visit will be assigned based on the study day slotting intervals as shown in the table below.
 - For records determined to be during the on-therapy period, use the study day with the slotting intervals in the table below to assign the records to the appropriate on-therapy analysis visit.
 - For records determined to be during the follow-up period, use the study day with the slotting intervals in the table below to assign the records to the appropriate follow-up period analysis visit.
 - For records determined to be during the individualized follow-up period, use the study day with the slotting intervals in the table below to assign the records to the appropriate individualized follow-up period analysis visit.

Table 9-1 Analysis Visit Windows

Scheduled Visit	Target Study Day of Visit	Slotting Intervals
Screening	-84 to -4	Not applicable
Baseline (Week 0)	1	-3 to 1 days
Week 2	15	2 to 22 days
Week 4	29	23 to 36 days
Week 6	43	37 to 50 days
Week 8	57	51 to 64 days
Week 10	71	65 to 78 days
Week 12	85	79 to 92 days
Week 14	99	93 to 106 days
Week 16	113	107 to 120 days
Week 18	127	121 to 134 days

Scheduled Visit	Target Study Day of Visit	Slotting Intervals
Week 20	141	135 to 148 days
Week 22	155	149 to 162 days
Week 24	169	163 to 176 days
Week 28	190	177 to 204 days
Week 32	218	205 to 232 days
Week 36	246	233 to 260 days
Week 40	274	261 to 288 days
Week 44	302	289 to 316 days
Week 48	330	317 to 344 days
Week 52	358	345 to 372 days
Week 56 *	386	373 to 400 days
Week 60** (End of Core Study Period) Subject has completed.	414	401 to 428 days

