* Week 56 is the end of treatment visit for those subjects completing the study per protocol. For subjects who withdraw early from active treatment, the end of treatment visit will be assigned to an analysis visit based on the visit slotting algorithm using study day and therapy period.

** Week 60 is the follow-up visit for those subjects completing the study per protocol. Subjects completing the study and meeting all entry criteria will be offered the option to participate in an extension study, which will start after completion of the Week 60 visit.

For parameters that were not scheduled to be collected at all visits, yet values are available, the visit intervals defined in the table above will be used to slot records. As previously noted for the baseline record, the last non-missing value before the start of treatment will be used for analysis. For post-baseline records, for parameters collected multiple times within a slotting interval, the assessment taken closest to the target study day will be used for analysis/summarization.

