12.6.1. Immunogenicity

A by-visit summary will present descriptive statistics for the actual and change from Baseline results by visit and treatment group for IgG, IgA, IgM, HAHA, high sensitivity C-reactive protein (hsCRP), and B-lymphocyte chemokine (BLC). Additionally, descriptive statistics will be used to summarize each subject's largest decrease from Baseline. The number and percentage of subjects below the LLN at each visit, below the LLN at any time during the on-therapy period and below the LLN during the first 12 weeks of treatment will be presented by treatment group.

All immunogenicity data will be presented in a data listing.

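### SAP 12.6 removes the protocol's by-arm counts of laboratory values of clinical concern and puts nothing in their place; separately, visit slotting can leave a transient ALT peak out of every by-arm lab table (minor, cheap to fix)

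*SAP*

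**What the plan says.** Protocol 6.3 lists as a safety endpoint: "Frequency of laboratory (hematology, chemistry, and urinalysis) results of potential clinical concern". Protocol 8.3.6.9 flags each value against the normal range and for potential clinical concern, and then plans the table: "The number and percentage of subjects with values in each of these categories at each assessment time point will be summarized".

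In SAP 2.2.4 the only endpoint for these three panels is "Change from Baseline in laboratory (hematology, chemistry, and urinalysis) parameters". SAP 12.6 states that quantitative "laboratory parameters with a quantitative result will be summarized, for each treatment group, at every assessed time point using descriptive statistics", adds change from baseline, and lists all results. It specifies no threshold count, shift table or worst value for hematology or chemistry. An any-time count does exist in SAP 12.6.1 (subjects "below the LLN at any time during the on-therapy period"), but only for IgG, IgA, IgM, HAHA, hsCRP and BLC.

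SAP 1 explains that the plan was reduced after early termination with 69 patients. SAP 2.2.1 adds: "Some of the analysis bullet points described in the original protocol is removed", pointing to sections 2.2.2 to 2.2.6.

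SAP 9.3.3 brings unscheduled and repeat draws into the windows: "For all records (including unscheduled visit records, early withdrawal records and repeat visit records), use the therapy period and study day determined above". One record per window then survives: "for parameters collected multiple times within a slotting interval, the assessment taken closest to the target study day will be used for analysis/summarization".

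**The concern.** There are two separate gaps.

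The first is a named protocol safety endpoint that loses its by-arm display. From the SAP text a reader could not learn, by arm, how many subjects ever reached ALT 3 or 5 x ULN or neutrophils <1 GI/L. These are the protocol's own monitoring and dose-hold cut-offs (Protocol Appendix 3 and 4.4.1).

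The second is that hematology and chemistry are summarized by arm only at slotted visits. Protocol Appendix 3 lets treatment continue with weekly liver tests when ALT is 3 to <8 x ULN, bilirubin is <2 x ULN, there are no relevant symptoms and weekly monitoring is possible. A higher value found at one of those checks may be the record that slotting discards.

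At stake is the completeness of the by-arm safety tables. No efficacy result is affected.

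**Working it through.** The plan gives no figure to reproduce here. The check applies SAP Table 9-1 and the closest-to-target rule to the protocol's own schedule.

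**Inputs.**
- Full chemistry at Weeks 12, 24, 36 and 48 (Protocol Table 6-1), on study day 7w + 1 + j, where j = -3 to +3 is the visit window: Days 85, 169, 253 and 337 at j = 0.
- Weekly ALT re-checks (Protocol Appendix 3).
- Slotting targets and intervals from SAP Table 9-1. From Week 28 on, the targets lie 7 days before 7w + 1 (Week 36: 246 against 253).
- Rule: in each window, keep the record with the smallest |day - target|.

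**One case.** Suppose ALT is 3.5, 7 and 2 x ULN on Days 253, 260 and 267. Days 253 and 260 both fall in the Week 36 window (233 to 260, target 246), at distances 7 and 14. Day 253 is kept. Day 267 belongs to Week 40. The 7 x ULN value enters no by-arm lab table.

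**Re-checks at +7, +14 and +21 days, j = 0.**

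| Visit | Check days | Kept | Dropped |
|---|---|---|---|
| Week 12 | 92, 99, 106 | 99 | 2 |
| Week 24 | 176, 183, 190 | 190 | 2 |
| Week 36 | 260, 267, 274 | 274 | 2 |
| Week 48 | 344, 351, 358 | 358 | 2 |

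Dropped: 2 + 2 + 2 + 2 = 8 of 12. This is unchanged for j = -3 to 0. For j = +1 to +3 it is 7 of 12, because the Week 12 +21 check moves into the Week 16 window and is kept. Adding a +28 check gives 2 + 3 + 3 + 3 = 11 of 16 at every j.

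**The +7 check when no later check follows.** Dropped at 4 of 4 visits for j = -3 to 0, and at 0 of 4 for j = +1 to +3. If a +14 check follows, the +7 check is dropped at 4 of 4 for every j.

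**The triggering value.** Kept at 4 of 4 visits for every j under weekly re-checks. An additional re-check 1 to 3 days later could displace it after an early Week 12 or Week 24 visit, but Appendix 3 does not ask for that while treatment continues.

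**Averaging of the triggering value.** With ULN 48 U/L (Protocol Appendix 13), 3 x ULN = 144 U/L. One such subject among n moves the arm mean by (144 - m)/n, where m is the mean of the others. Assuming n of 20 to 35 and m of 15 to 40 U/L: (144 - 40)/35 = 3.0 and (144 - 15)/20 = 6.5 U/L. This applies only at a scheduled chemistry visit. The retained re-checks fall in the Week 14, 16, 28, 40 or 52 windows, where no chemistry is scheduled, so they are not diluted in this way.

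**Neutrophils.** Assume a repeat 1 to 7 days after each scheduled count at Weeks 4 to 56, with other visits on nominal days: 14 visits x 7 days = 98 pairs. The repeat is dropped in:
- 98 of 98 pairs at j = 0;
- 93, 88 and 83 at j = +1, +2 and +3;
- 86, 74 and 62 at j = -1, -2 and -3 if an exact tie is not counted as a loss, or 92, 80 and 68 if the earlier record wins. The SAP gives no tie rule.

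The repeat displaces the scheduled count in 0 pairs for j = 0 to +3, and in 6, 18 and 30 pairs for j = -1, -2 and -3.

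**The case against.** The strongest reply has five parts.

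1. The two gaps should not be joined. A reader might infer that dropping the clinical-concern counts is what loses the peak. It is not: Protocol 8.3.6.9 planned those counts per time point and Protocol 8.3.6.3 left visit slotting to the analysis plan, so restored counts on slotted data would miss the same value. This stands.
2. A reader might infer an undisclosed departure from the protocol. SAP 1 and 2.2.1 disclose a deliberate reduction that covers 2.2.4. This stands, although the reasons in SAP 1 (subgroups, multiplicity, small sample) do not speak to a descriptive count.
3. Much stays visible by arm: discontinuations under protocol-defined stopping criteria (SAP 10.1), Hy's Law cases as SAEs, and abnormalities the investigator judged clinically significant and recorded as AEs (Protocol 6.3.3). All laboratory values and liver event data are listed, and with 69 patients a listing can be counted by hand. This narrows the gap but does not close it. An asymptomatic ALT of 5 to <8 x ULN that resolves within 2 weeks, or 3 to <5 x ULN within 4 weeks, leads only to monitoring, and AE recording rests on judgment.
4. The fractions count check dates, and the neutrophil figures rest on assumed repeat timing. This stands.
5. The table shells are separate documents and may contain more. This stands; the point concerns the SAP text.

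**Conclusion.** The point holds as a minor reporting gap. By the SAP text, a protocol-named laboratory endpoint has no by-arm threshold count for hematology or chemistry. Independently, slotting can remove a transient ALT peak from all by-arm lab tables: 7 or 8 of 12 check dates at +7 to +21 days, and 11 of 16 with a fourth check. These are not proportions of subjects or of peaks, and the documents give no basis for estimating how often a peak follows the trigger.

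The documents do not support reading this as a concealed safety signal or as an error in the slotting rule. One record per window is normal for by-visit statistics. What remains is mainly asymptomatic, self-resolving ALT of 3 to <8 x ULN, and neutrophils <1 GI/L that were not recorded as AEs.

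**What to change.** Keep SAP 9.3.3 for by-visit statistics. Add to SAP 12.6 one descriptive table by arm, using each subject's worst on-therapy value (period as in SAP 9.3.2) from all scheduled and unscheduled records. It should give the number and percentage of subjects with:
- ALT >=3, >=5 and >=8 x ULN;
- bilirubin >=2 x ULN;
- neutrophils <1 GI/L;
- AST, platelets, hemoglobin and WBC outside the normal range.

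State in SAP 12.6 that this table replaces the protocol's per-time-point clinical-concern counts for these key parameters, and that the remaining counts are dropped because of early termination.

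The cost is one extra table from data already collected and two sentences of text. Restoring the per-visit counts alone would not be enough, since they would still run on slotted records.
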